7.6 Unscheduled Visit

An unscheduled visit may be performed at any time at the discretion of Investigator in order to further evaluate a subject. The specific assessments to be performed at these visits would be determined by the Investigator according to nature of the subject specific follow-up required, however at a minimum the assessments would include the following:

- Vital signs (temperature, heart rate, respiration rate and blood pressure)
- Symptom-directed physical examination
- Review concomitant medications

- Review AEs
- Laboratory analyses (additional details are provided in the Laboratory Manual):
 - Safety Labs: Chemistry, hematology, coagulation, urinalysis, urine drug test, and urine pregnancy test (if positive on dipstick, serum pregnancy test should be performed).
 - Virology/Immunology: HBV DNA, HBV pgRNA, HBsAg, HBeAg, HBcrAg, sample for HBV sequencing and HBV nucleic acids
 - PK Samples: Samples for ABI-H2158 or PBO and ETV can be collected at the same time with other labs. See [Section 7.8.8](#) for additional information on PK sampling.

Assessments performed should be documented in the subject's source documentation. Clinical laboratory assessments should be conducted through the central laboratory.

7.7 Premature Termination Visit

Should a subject prematurely discontinue treatment ([Section 7.9.1](#)) or discontinue from the study ([Section 7.9.2](#)), a Premature Termination visit should be scheduled. While the Investigator may include additional assessments and evaluations determined by the status of the individual subject, at the minimum, the following assessments should be performed as soon as feasibly possible:

- Vital signs (temperature, heart rate, respiration rate and blood pressure)
- Complete physical examination (excluding breast and genitalia unless indicated)
- 12-lead ECG
- Review concomitant medications
- Review AEs
- Review dosing diary and assess drug accountability (if applicable)
- Laboratory analyses (additional details are provided in the Laboratory Manual):
 - Safety Labs: Chemistry, hematology, coagulation, urinalysis, urine drug test, and urine pregnancy test (if positive on dipstick, serum pregnancy test should be performed).
 - Virology/Immunology: HBV DNA, HBV pgRNA, HBsAg, HBeAg, HBcrAg, HBsAb and HBeAb, sample for HBV sequencing and HBV nucleic acids
 - PK Samples: Samples can be collected at the same time with other labs. See [Section 7.8.8](#) for additional information.

7.8 Study Assessments

This section describes evaluations and procedures to be performed and items to be recorded or available on source documents. Data from some required evaluations may not be required to be recorded on case report forms (e.g. laboratory results). For further details, refer to [Appendix 1](#).

7.8.1 Demographics, Medical and HBV History

Demographic characteristics including age, race, and ethnicity will be recorded. The Investigator or designee will collect a complete medical, surgical, and HBV history at Screening. Any changes to medical, surgical, and HBV history since Screening will also be recorded for the duration of the study.

Height (cm) and body weight (kg) without shoes will be measured and BMI will be calculated using the height obtained at Screening. The subject's BMI will be calculated using metric units and rounded to the nearest whole number according to the following formula: $BMI = \text{weight (kg)} / (\text{height [m]})^2$.

7.8.2 Liver Staging

Liver staging is to be performed to determine lack of cirrhosis or advanced liver disease as required by inclusion criteria (see [Section 5.2](#)). The methods for noninvasive, simple, and painless procedures are (1) Fibroscan (if available) or (2) Magnetic Resonance elastography (MRE). The Medical Monitor may be contacted for questions concerning liver staging.

7.8.3 Physical Examination

Complete physical examinations will be performed by the Investigator or qualified Sub-Investigator at the protocol designated timepoints. The complete physical examination will consist of the following body systems: head, eyes, ears, nose, and throat; cardiovascular; respiratory; gastrointestinal; dermatologic; musculoskeletal; nervous; extremities; and lymph nodes. Additional body systems may be evaluated at the Investigator's discretion. Examination of the breast and genitalia are not required unless clinically indicated.

Additional symptom-directed physical examinations will be performed at the protocol designated timepoints. Additional symptom-directed of complete physical examinations made be performed at the Investigator's discretion throughout the course of the study. If the subject reports feeling unwell or has ongoing AEs, the Investigator or qualified Sub-Investigator will examine the appropriate body system(s).

7.8.4 Electrocardiograms

A standard 12-lead ECG will be obtained as specified in the Schedule of Assessments ([Appendix 1](#)). Prior to the conduct of the 12-lead ECG, subjects should rest in a supine position for 10 mins. ECGs should be conducted in accordance with local practice and equipment. The ECG assessment will include interpretation of the tracings (eg, rhythm, presence of arrhythmia or conduction defects, morphology, any evidence of myocardial infarction, or ST segment, T-wave, and Uwave abnormalities). The Investigator or a physician Sub-Investigator is responsible for reviewing and overreading the ECG interpretation, for assessing whether the ECG machine interpretation findings are accurate, appropriate,

normal or abnormal, and for providing corrected interpretations as appropriate. In addition, any abnormal ECGs will be assessed for clinical significance.

Additional ECGs may be obtained if clinically indicated and will be obtained if abnormal and clinically significant or thought to be an error (eg, lead placement error, movement artifact, etc.). Any additional relevant data obtained by the Investigator during the course of this study will be recorded in the subject's source documentation. The Investigator or a physician Sub-Investigator will review all ECGs, evaluate the results, and sign/date the tracing or report. For any ECG abnormality that the Investigator considers clinically significant, the Investigator will:

- Repeat the ECG;
- Obtain follow-up ECG(s) if any significant abnormalities are detected after study drug administration to document resolution and as clinically indicated;
- Record as an AE any ECG abnormality that: (1) is confirmed and the Investigator considers clinically significant; (2) requires a subject to be discontinued from the study; or (3) the abnormality requires a subject to receive treatment. ([Section 8](#)).

7.8.5 Vital Signs

Vital signs will include temperature, heart rate, respiration rate, and blood pressure at timepoints specified in the Schedule of Assessments in [Appendix 1](#).

7.8.6 Clinical Laboratory Tests

Clinical laboratory tests will be performed at the designated Central laboratories at the timepoints indicated in the Schedule of Assessments table in [Appendix 1](#). Should any laboratory parameter require urgent testing to support immediate medical care of a subject, samples should be collected for both local and central laboratory assessment. The local result may be used to manage the emergent medical situation, however only the results from the central laboratory will be reported in the study database for analysis purposes.

The specific components of the clinical laboratory tests are listed below in [Table 5](#).

Table 5: Clinical Laboratory Tests

Panel	Tests
Clinical Chemistry	Blood glucose levels, serum or plasma electrolytes (sodium, potassium, chloride, bicarbonate), calcium, creatine kinase, blood urea nitrogen, creatinine, uric acid, total and direct bilirubin ^a , ALT, AST, GGT, alkaline phosphatase, LDH, amylase, triglycerides, total cholesterol, inorganic phosphate or total phosphate, total protein, albumin, lipase, and total serum or plasma globulins
In case of ALT Elevation	ALT, AST, total bilirubin, serum albumin, creatine kinase, and INR
Hematology	Complete blood counts: hemoglobin, hematocrit, RBC indices (MCV, MCHC), reticulocyte counts, leukocyte counts (total and differential), and platelet counts

Panel	Tests
Coagulation	Prothrombin time/INR and aPTT
Urinalysis	pH, specific gravity, protein, glucose, ketones, and occult blood
Other	AFP, HbA1c, and FSH (ALL Females regardless of fertility status)
Pregnancy tests	For females only; a serum pregnancy test must be performed at Screening. On Day 1, urine and serum pregnancy test should be performed predose. Subject may begin treatment based on urine results. Any subject negative by urine subsequently found to be positive on serum should immediately discontinue treatment. All post-Day 1 pregnancy tests may be conducted by urine dipstick. If positive on dipstick, reflex to serum. A positive result disqualifies the subject for study treatment.
Urine drug Screening	Amphetamine/methamphetamine, barbiturates, benzodiazepines, cocaine metabolite, ethanol, opiates, phencyclidine, and propoxyphene.
Antibodies	HCV, HDV, HAV IgM, HEV IgM, and HIV

AFP: alpha fetoprotein; ALT: alanine aminotransferase; aPTT: activated partial thromboplastin time; AST: aspartate aminotransferase; FSH: follicle-stimulating hormone; GGT: gamma-glutamyl transpeptidase; HAV: hepatitis A virus; HbA1c: hemoglobin A1c; HCV: hepatitis C virus; HDV: hepatitis D virus; HEV: hepatitis E virus; HIV: human immunodeficiency virus; IgM: immunoglobulin M; INR: International Normalized Ratio; LDH: lactate dehydrogenase; MCHC: mean corpuscular hemoglobin concentration; MCV: mean corpuscular volume; RBC: red blood cell; ULN: upper limit of normal.

^a Perform fractionated bilirubin if total bilirubin >ULN.

7.8.7 HBV Virology

To provide an assessment of the antiviral efficacy of ABI-H2158 in subjects with CHB, this study will evaluate treatment effects on the following parameters:

- HBV genotyping
- HBV DNA
- HBV pgRNA
- HBsAg
- HBeAg
- HBcrAg
- HBsAb
- HBeAb
- HBcAb
- HBV sequence analysis for assessment of resistance

To ensure standardization of the virologic methodologies utilized in this study, HBV DNA-related, HBV antigen-related and HBV antibody-related virologic assessments will be conducted at a central reference laboratory. Subject serum samples for resistance-related sequencing and HBV pgRNA testing will be shipped frozen to the Sponsor or a designated third-party laboratory for testing. The HBV virology tests will be performed at the timepoints indicated in the Schedule of Assessments table in [Appendix 1](#). HBV pgRNA results could unblind individual subject's treatment assignments and therefore will not be

reported to investigative sites or other blinded personnel until completion of the study, the database has been locked and the study has been unblinded.

Additional details concerning the collection and processing of HBV virology samples are described in the Laboratory Manual.

7.8.8 Pharmacokinetic Assessments

During the study, predose plasma samples will be collected from all subjects to explore the PK profile of ABI-H2158 and ETV following combination treatment in subjects with CHB. Additionally, postdose samples will be collected. The timing of PK sample collection is outlined in [Table 6](#). Additional details regarding the collection, processing, storage, and shipment of PK samples are described in the Laboratory Manual.

Table 6: Pharmacokinetic Sample Collection

Time Period	Time Relative to Study Drug Administration ^a	Study Visit
Treatment	Predose	Day 1, Weeks 4, 48, and 72
	30 min to 2 hours postdose	Weeks 2, 8, 12, 24, and 28
	2 to 4 hours postdose	Day 1
	4 to 6 hours postdose	Weeks 16 and 20
Follow-up	Collect at same time with other central labs	At Unscheduled and Premature Termination Visits and the Week 4 Post Treatment Follow-up visit

^a Sample collection times are targeted times. Samples collected outside of these targeted times will not be considered protocol deviations. The actual sample collection date/time should be accurately recorded on source documentation. If the subject administers study drug at home, a pharmacokinetic sample should be collected during the visit with documentation of date and time of the dose in the subject's source documents.

7.9 Discontinuation

A subject may withdraw from the study at any time at his/her own request or may be withdrawn at any time at the discretion of the Investigator or Sponsor for safety, behavioral, compliance, or administrative reasons. This is expected to be uncommon. At the time of discontinuing from the study, if possible, a Premature Termination visit should be conducted ([Section 7.7](#)). If the subject withdraws consent for disclosure of future information, the Sponsor may retain and continue to use any data collected before such a withdrawal of consent. If a subject withdraws from the study, he/she may request destruction of any samples taken and not tested, and the Investigator must document this in the site study records.

7.9.1 Discontinuation From Treatment

If an individual subject is not satisfactorily tolerating study drug treatment due to AEs in the judgment of the Investigator, then – in consultation with the Sponsor - the subject may discontinue treatment with ABI-H2158 or PBO. ETV may be continued at the discretion of the Investigator. A subject also has the

right to discontinue treatment with AHI-H2158 or PBO due to his/her wish. Discontinuation from treatment does not mean discontinuation from the study. Subjects who prematurely discontinue treatment should immediately undergo the assessments listed for the Premature Termination visit ([Section 7.7](#)) and then continue scheduled follow-up assessments.

If a subject is determined to have developed substitutions in HBV Cp gene sequences associated with viral resistance or blunted treatment response ([Section 7.11](#)), then they will discontinue treatment with ABI-H2158 or PBO. ETV may be continued at the discretion of the Investigator. Subjects who prematurely discontinue treatment should immediately undergo the assessments listed for the Premature Termination visit ([Section 7.7](#)) and then continue scheduled follow-up assessments.

In this study, subjects will be closely monitored for any evidence of worsening hepatic function. Procedures to be followed for these subjects are described in [Section 9.4](#). Study treatment will be discontinued in subjects with confirmed evidence of declining hepatic function during treatment, a Premature Termination visit ([Section 7.7](#)) will be completed and subjects will subsequently undergo the follow-up assessments described in [Section 7.5](#).

Any subjects negative by urine pregnancy test at Baseline (Day 1) who are subsequently found to be positive on serum pregnancy test should immediately discontinue treatment with ABI-H2158 or PBO. ETV may be continued if indicated based on Investigator judgment in accordance with local practice and the approved ETV package insert. These subjects may be replaced at the discretion of the Sponsor.

7.9.2 Discontinuation From Study

Discontinuation from study (ie, withdrawal of consent) means that the subject does not wish to receive further protocol-required treatments or undergo protocol-required procedures, and the subject does not wish to, or is unable to continue further study participation. Subjects who discontinue from the study during follow-up should undergo the assessments listed for the Premature Termination visit ([Section 7.7](#)). Subject data up to withdrawal of consent will be included in the analysis of the study, and where permitted, publicly available data can be included after withdrawal of consent.

7.9.3 Subjects Lost to Follow-up

A subject will be considered lost to follow-up if they repeatedly fail to return for scheduled visits and is unable to be contacted by the study site. The following actions must be taken if a subject fails to return to the clinic for a required study visit:

- The site must attempt to contact the subject, reschedule the missed visit as soon as possible, and counsel the subject on the importance of maintaining the assigned visit schedule and ascertain whether or not the subject wishes to and/or should continue in the study.
- Before a subject is deemed lost to follow-up, the Investigator or designee must make every effort to regain contact with the subject (where possible, 3 telephone calls and, if necessary, a certified letter to the subject's last known mailing address or local equivalent methods). These contact attempts should be documented in the subject's medical record.

Should the subject continue to be unreachable, they will be considered lost to follow-up.

7.10 End of Study Definition

The study will be completed when the last subject completes the 24 Weeks Post Follow-up period, or is considered “lost to follow-up,” (Section 7.9.3) whichever is later.

7.11 Resistance Monitoring

To assess potential HBV Cp gene sequences associated with viral resistance or blunted treatment response, serum samples from subjects at each visit will be collected (Section 7). Samples from those subjects with evidence of nonresponse to treatment, such as viral breakthrough (ie, $\geq 1 \log_{10}$ increase in on-treatment HBV DNA from on-treatment nadir) or if there is no apparent and consistent decline in HBV nucleic acids throughout the study, will be selected for HBV Cp gene sequencing, with sequence comparisons to baseline sequences, as well as comparisons to Cp gene sequences from subjects who received PBO and HBV database sequences.

7.12 Use of Subject Samples for Exploratory Objectives Research

With the subject’s approval and as approved by local IRBs/IECs and Country Regulatory Agencies, biological samples collected to assess the relationship between new and known viral biomarkers and virologic and/ or clinical outcomes, will be stored by the Sponsor or their designee. Apart from the analysis described in exploratory objectives (Sections 3.1.3 and 3.2.3), these samples could be used to research CHB, its complications, and other conditions for which individuals with CHB are at increased risk, and to improve treatment. The Sponsor will also have a code-link that will allow linking the biological specimens with the phenotypic data from each subject, maintaining the blinding of the identity of the subject.

8 ADVERSE EVENTS

An AE is any untoward medical occurrence in a study subject administered an investigational product(s) regardless of the causal relationship with treatment.

An AE, therefore, can be any unfavorable and unintended sign (including laboratory finding), symptom, or disease temporally associated with participation in an investigational study, whether or not considered drug-related. In addition to new events, any increase in the severity or frequency of a pre-existing condition that occurs after the subject signs the ICF for participation is considered an adverse event. This includes any side effect, injury, toxicity, or sensitivity reaction.

8.1 Documenting Adverse Events

Adverse events will be monitored throughout the entire study. Investigators will ask the subject at each visit if they have experienced any untoward effects since the last study visit. All AEs will be entered in the electronic case report forms (eCRFs) provided: a description of the event, severity, time of occurrence, duration, any action (eg, treatment and follow-up tests), and the outcome should be provided along with the Investigator's assessment of the relationship to the study treatment.

Adverse events will be recorded from the time written informed consent is signed through end of study (completion of follow-up period).

8.2 Assessment of Intensity

The severity of each AE and laboratory abnormality is to be assessed by the Investigator according to the modified Division of AIDS (DAIDS) Table for Grading the Severity of Adult and Pediatric AEs ([Appendix 2](#)), which grades the severity of clinical AEs and laboratory abnormalities in a 4-category system.

For AEs not included in [Appendix 2](#), the following guidelines will be used to describe severity:

- **Mild (Grade 1):** Mild symptoms causing no or minimal interference with usual social & functional activities with intervention not indicated
- **Moderate (Grade 2):** Moderate symptoms causing greater than minimal interference with usual social & functional activities with intervention indicated
- **Severe (Grade 3):** Severe symptoms causing inability to perform usual social and functional activities with intervention or hospitalization indicated (Of note, the term "severe" does not necessarily equate to "serious")
- **Life-Threatening (Grade 4):** Potentially life-threatening symptoms causing inability to perform basic self-care functions with intervention indicated to prevent permanent impairment, persistent disability, or death

Note that an AE or laboratory abnormality that is life-threatening as it exists constitutes an SAE.

8.3 Assessment of Causality

All AEs must have their relationship to study intervention assessed by the clinician who examines and evaluates the subject based on temporal relationship and his/her clinical judgment. Each AE must be recorded in the source documentation, whether serious or not serious. For the purposes of this study each event is to be assessed with regard to the following causality categorizations, in the Investigator's considered judgment:

- **Not related:** An AE with sufficient evidence to accept that there was no causal relationship to administration of study drug (eg, no temporal relationship because the study drug was administered after the onset of the event, an investigation showed that study drug was not administered, another cause was proven).
- **Related:** An AE occurred in a plausible time relationship to administration of study drug and that could not be explained by a concurrent disease or other drugs or events. The response to withdrawal of the drug (dechallenge) was clinically reasonable.

8.4 Expectedness

An AE is considered "unexpected" if it is not listed in the IB or is not listed at the specificity or severity that has been observed. The CRO and Sponsor Medical Monitors will be responsible for determining whether an AE is expected or unexpected.

8.5 Abnormal Laboratory Test Values

In the event of abnormal laboratory test values, the tests should be repeated immediately. If the Investigator considers the abnormality to be clinically significant, it should be reported as an AE and followed up until it returns to the normal range and/or an adequate explanation of the abnormality is found.

8.6 Adverse Event Follow-up

After the initial AE or SAE report, the Investigator will follow-up proactively on each subject and provide further information to the CRO/Sponsor on the subject's condition. During the study, all AEs or SAEs should be followed up to resolution unless the event is considered by the Investigator to be unlikely to resolve due to the subject's underlying disease, or the subject is lost to follow-up.

8.7 Pregnancy

8.7.1 Female subjects who become pregnant

Any female subject who becomes pregnant while participating in the study including the 24-week follow-up period will discontinue the study drug(s) immediately. The subject will be followed to determine the outcome of the pregnancy. The Investigator will collect follow-up information on the subject and the neonate for 6 to 8 weeks after birth. Any termination of pregnancy will be reported, regardless of fetal status (presence or absence of anomalies) or indication for the procedure.

The Investigator must inform the Sponsor of the pregnancy. The initial information will be recorded on the Pregnancy Reporting form and submitted to the CRO Pharmacovigilance group within 24 hours of learning of a subject's pregnancy.

While pregnancy itself is not considered to be an AE or SAE, any pregnancy complication or elective termination of a pregnancy for medical reasons will be reported as an AE or SAE. A spontaneous abortion (occurring at <22 weeks gestational age) or still birth (occurring at >22 weeks gestational age) is always considered to be an SAE and will be reported as such.

Any post-study pregnancy related SAE considered reasonably related to the study drug(s) by the Investigator will be reported to the Sponsor. While the Investigator is not obligated to actively seek this information in former study subjects, he or she may learn of an SAE through spontaneous reporting.

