4 STUDY PLAN

4.1 Study Design

This Phase 2a, multicenter, randomized, single-blind (ie, investigational site and subjects are blinded), PBO-controlled study will assess the safety, antiviral activity, and PK of ABI-H2158 administered QD in combination with ETV in subjects with CHB. It is planned that multiple parallel cohorts will be enrolled in the study.

[figure not shown]
The first treatment cohort will evaluate ABI-H2158 300 mg in combination with ETV (n=30) compared to ETV alone (n=10) in treatment-naïve subjects with HBeAg positive CHB. The second treatment cohort will evaluate ABI-H2158 300 mg in combination with ETV (n=30) compared to ETV alone (n=10) in treatment-naïve subjects with HBeAg negative CHB. Additional cohorts may be added by future protocol amendment(s) based, in part, upon emergent safety, antiviral activity, and PK data from the ABI-H2158 regimens evaluated in the ongoing Phase 1b study ABI-H2158-101 ([Section 2.2.3.1](#)).

In Cohort 1, subjects will be randomized in a 3:1 ratio to receive 300 mg ABI-H2158+ETV (n=30) or matching PBO+ETV (n=10) for 72 weeks ([Figure 1](#)). Treatment assignments will be stratified by the HBV DNA level measured at the Screening visit (ie, $\geq 8.0 \log_{10}$ IU/mL versus $< 8.0 \log_{10}$ IU/mL). After completing treatment at Week 72, or following premature treatment discontinuation, all subjects will enter a 24-week follow-up period. During the follow-up period all subjects will remain on ETV and undergo the follow-up assessments described in [Section 7.5](#). After completing the 24-week follow-up period, all subjects will resume management by their treating physician in accordance with local standard of care.

In Cohort 2, subjects will be randomized in a 3:1 ratio to receive 300 mg ABI-H2158+ETV (n=30) or matching PBO+ETV (n=10) for 72 weeks ([Figure 1](#)). Treatment assignments will be stratified by the HBV DNA level measured at the Screening visit (ie, $\geq 6.0 \log_{10}$ IU/mL versus $< 6.0 \log_{10}$ IU/mL). After completing treatment at Week 72, or following premature treatment discontinuation, all subjects will enter a 24-week follow-up period. During the follow-up period all subjects will remain on ETV and undergo the follow-up assessments described in [Section 7.5](#). After completing the 24-week follow-up period, all subjects will resume management by their treating physician in accordance with local standard of care.

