4.3 Study Treatment

This study is designed to evaluate the safety, PK, and antiviral activity of various ABI-H2158-containing regimens in subjects with CHB. These regimens will be evaluated in multiple treatment cohorts. Cohort 1 will enroll treatment-naïve subjects with HBeAg positive CHB and Cohort 2 will enroll treatment-naïve subjects with HBeAg negative CHB.

The study treatment (ABI-H2158 or PBO) will be administered in combination with a standard-of-care known effective therapy (ETV). All subjects will receive ABI-H2158 or matching PBO as three 100 mg tablets QD. ETV will be administered as a single 0.5 mg tablet QD. ABI-H2158, matching PBO, and ETV will be administered on an empty stomach (at least 2 hours after a meal and 2 hours before the next meal) at approximately the same time each day. Further information is provided in the ETV package insert. On study visit days, ABI-H2158 or PBO will be administered in the clinic; subjects will self-administer assigned treatment on all other days. On study visit days which include PK collection ([Section 7](#)), subjects will administer ABI-H2158 or PBO and ETV in the clinic except for Week 16 and Week 20. Study personnel will document the time of study drug administration in the subject's medical record. Subjects will be required to record the dates and times of each dose of study drug (ie, ABI-H2158 or PBO and ETV) they self-administer in the dosing diary provided to them at the Day 1 visit.

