4.4 Duration of Treatment

All subjects will receive their randomized treatment assignment in a blinded manner for up to 72 weeks. After completing treatment at Week 72, or following premature treatment discontinuation, all subjects will enter a 24-week follow-up period. During the follow-up period all subjects will remain on ETV and undergo the follow-up assessments described in [Section 7.5](#). After completing the 24-week follow-up period, all subjects will resume management by their treating physician in accordance with local standard of care.

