6.3 Description and Handling of Entecavir

All subjects participating in this study will initiate and continue oral administration of 0.5 mg ETV tablets, QD, for the duration of the study. ETV tablets will either be provided by Assembly Biosciences or sourced locally by the site. Provision of ETV for the purposes of the study will be discussed and agreed with each investigational site prior to study conduct. Details describing the packaging, labelling, storage, and handling of ETV are described in the package insert.

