7.5 Follow-up Assessments

All subjects who complete treatment per protocol or prematurely discontinue treatment will enter a 24-week follow-up period during which they will have the following assessments performed at 4, 8, 12, and 24 weeks (± 5 days) after the last dose of ABI-H2158 or PBO unless otherwise stated:

- Measure body weight (24 Weeks post only)
- Vital signs (temperature, heart rate, respiration rate and blood pressure)
- Complete physical examination (24 Weeks post only)
- Symptom-directed physical examination (not at 24 Weeks post)
- 12-lead ECG (24 Weeks post only)
- Review concomitant medications
- Review AEs
- Assess drug accountability (for ETV)
- Study drug dispensation (for ETV, 4 Weeks post and 12 Weeks post only)
- Laboratory analyses (additional details are provided in the Laboratory Manual):
 - Safety Labs: Chemistry, hematology, coagulation, urinalysis (4 Weeks post, 12 Weeks post, and 24 Weeks post only), and urine pregnancy test (if positive on dipstick, serum pregnancy test should be performed [4 Weeks post only]).
 - Virology/Immunology: HBV DNA, HBV pgRNA, HBsAg, HBeAg, HBcrAg, HBsAb and HBeAb (24 Weeks post only) sample for HBV sequencing and HBV nucleic acids
 - PK Sample: Sample for ETV can be collected at the same time with other labs (4 Weeks post only)

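### Protocol 8.7.1 makes a subject who becomes pregnant stop ETV with no discretion, whereas 7.9.1 leaves ETV to the Investigator and the general rule keeps everyone on it

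*Combined protocol and SAP*

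**What the plan says.** Protocol 8.7.1 covers any female subject "who becomes pregnant while participating in the study including the 24-week follow-up period will discontinue the study drug(s) immediately". It then deals with following the pregnancy and the neonate. It says nothing separate about ETV.

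Protocol 7.9.1 has its own pregnancy paragraph, for subjects with a negative urine test on Day 1 and a later positive serum test. They stop ABI-H2158 or placebo, and "ETV may be continued if indicated based on Investigator judgment in accordance with local practice and the approved ETV package insert". For stops due to adverse events or resistance, 7.9.1 likewise says "ETV may be continued at the discretion of the Investigator".

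The general rule on ETV is unconditional. Section 4.4 states: "During the follow-up period all subjects will remain on ETV". Section 4.1 says the same for each cohort. Under 6.3 all subjects "will initiate and continue oral administration of 0.5 mg ETV tablets, QD, for the duration of the study". Appendix 1 footnote e repeats the rule for the 24-week follow-up, and SAP 1.2 carries it into the 12-week follow-up used after early termination. None of these places mentions pregnancy.

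On what counts as study drug, 4.3 has subjects record "each dose of study drug (ie, ABI-H2158 or PBO and ETV) they self-administer". Protocol 6.5 and SAP 3.6.1 also include ETV.

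**The concern.** Subjects in this trial have chronic hepatitis B and entered with measurable viremia. Read as written, 8.7.1 withdraws the only antiviral that a pregnant subject in follow-up is taking, with no room for clinical judgment. Another section of the same protocol leaves that decision to the Investigator. A site that looks up pregnancy in 8.7.1 and a site that looks it up in 7.9.1 could treat the same patient differently.

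Monitoring after such a stop is also thinly specified. Follow-up visits run from a fixed point, "after the last dose of ABI-H2158 or PBO unless otherwise stated", so stopping ETV does not trigger one. Section 9.4 calls for close ALT follow-up after study drug ends, but sets visit intervals only once ALT has risen.

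**Working it through.** The plan gives no figure to reproduce. The check is mainly a comparison of clauses, followed by two small calculations on size.

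1. **Does 8.7.1 reach ETV?** Sections 4.3 and 6.5 and SAP 3.6.1 count ETV as study drug. Footnote e limits dispensing from Week 72 onwards to ETV. By follow-up, ABI-H2158 or placebo has already ended, so the follow-up part of 8.7.1 would have no effect unless it meant ETV. Where 7.9.1 means the core inhibitor alone, it names ABI-H2158 or placebo.

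2. **Does 7.9.1 resolve it?** Its pregnancy paragraph can be read in two ways.
   - Narrow reading: it concerns discordant urine and serum tests on Day 1, as in Table 5 and Appendix 1 footnote h. A subject already pregnant on Day 1 may then keep ETV, while one who becomes pregnant later must stop it.
   - Broad reading: every eligible woman is urine-negative on Day 1 (inclusion criterion 3), and every later positive dipstick goes to a serum test. The paragraph then also covers later pregnancies, and 7.9.1 and 8.7.1 give different ETV instructions for the same subject.

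   Neither reading removes the inconsistency.

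3. **Relation to the general rule.** A specific pregnancy clause can be taken as an exception to the stay-on-ETV text. That text, however, does not refer to 8.7.1 or 7.9.1.

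4. **Visit timing.** Follow-up visits are at 4, 8, 12 and 24 weeks after the last ABI-H2158 or placebo dose. The only scheduled follow-up pregnancy test is at 4 weeks. If pregnancy is found there, the next visit, with chemistry and HBV DNA, is 8 − 4 = 4 weeks later. The longest gap, 24 − 12 = 12 weeks, needs ETV to stop at the 12-week visit.

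5. **Week 24 analysis.** SAP 3.6.2 ends the on-treatment period at the last ABI-H2158 or placebo dose. A pregnancy in follow-up comes after that date and cannot enter the Week 24 comparison.

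6. **Follow-up HBV DNA summary, as an illustration.** Assume one subject stops ETV and goes from below LLOQ to the entry minimum, with all randomized subjects observed. Shift in arm mean = rebound / n. Entry minima are log10(2×10^5) = 5.301 (Cohort 1) and log10(2×10^3) = 3.301 (Cohort 2). SAP 3.4 sets a value below LLOQ to LLOQ minus 1 unit. The LLOQ is not in the documents. An assumed 20 IU/mL gives log10(19) = 1.279.
   - Cohort 1: 5.301 − 1.279 = 4.022; /10 = 0.40 (placebo), /30 = 0.13 (ABI-H2158).
   - Cohort 2: 3.301 − 1.279 = 2.022; /10 = 0.20, /30 = 0.07.
   - For LLOQ from 10 to 100 IU/mL, placebo ranges are 0.33 to 0.43 (Cohort 1) and 0.13 to 0.23 (Cohort 2). ABI-H2158 ranges are 0.11 to 0.14 and 0.04 to 0.08.

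   Half the rebound gives half the shift, and no affected subject gives none.

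**The case against.** The strongest reply is that a specific safety rule ordinarily governs a general one, so 8.7.1 is simply an exception to the stay-on-ETV text. This stands against calling the two irreconcilable. It does not help the clause itself, because the exception is then a compulsory ETV stop that 7.9.1 does not impose.

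A second reply is that the term study drug is used loosely. Section 4.3 also describes ABI-H2158 or placebo as the study treatment given alongside standard-of-care ETV. Section 9.4 speaks of study drug ending at a point where ETV continues. The authors may not have meant ETV. That is possible, but the explicit mention of follow-up in 8.7.1 then has nothing to act on, and a site cannot tell which meaning applies.

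A reader might infer that the subject is left unmonitored and untreated. The documents do not support that. Unscheduled Visits are allowed at any time (7.6), the Investigator may prescribe for emergent events (6.4), and 8.7.1 follows the subject to the pregnancy outcome. Dual contraception is required through follow-up (Appendix 3). The 12-week gap is a chosen worst case.

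A reader might also infer that the SAP is in error because nothing marks HBV DNA or laboratory records taken after ETV stops. That does not hold either. The affected output is a descriptive summary of all observed data, and the SAP nowhere presents it as on-ETV only. ETV non-completion with reasons, ETV exposure and the by-subject administration listings already identify such subjects.

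**Conclusion.** The inconsistency holds and is minor. Protocol 8.7.1 requires ETV to stop in a subject who becomes pregnant, follow-up included, with no discretion and no named replacement. Section 7.9.1 allows ETV to continue, and the stay-on-ETV text does not acknowledge either provision. The conclusion rests on ETV being study drug under 4.3 and 6.5 and on its being the only study drug dispensed in follow-up.

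The consequence is for the care of an individual patient. The number of such patients is not given and may be zero. The Week 24 primary analysis is unaffected by a follow-up pregnancy. The shifts worked out above depend on an assumed LLOQ and rebound, and do not show a fault in the SAP. Development stopped on 01 September 2021, so the protocol wording now matters only for a pregnancy in whatever follow-up remains.

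**What to change.** - In 8.7.1, state that the subject stops ABI-H2158 or placebo immediately. State that ETV may be continued, or replaced by other HBV treatment, on the Investigator's judgment in line with local practice and the ETV package insert.
- Add that if ETV is stopped without replacement, ALT and HBV DNA are monitored by Unscheduled Visits at the Investigator's discretion. The documents give no basis for insisting on a fixed interval.
- In 4.1, 4.4, 6.3 and Appendix 1 footnote e, cross-refer to 7.9.1 and 8.7.1 as exceptions to remaining on ETV.

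The cost is a short rewording of 8.7.1 and one cross-reference in four places. Optionally, before database lock, the by-subject laboratory and virology listings could mark records dated after the last ETV dose. SAP 3.6.1 already derives that date, so no new data are needed.
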